4. TRIAL OBJECTIVES

The purpose of this study is to provide data on the safety and efficacy of Theranova 400 dialyzer compared Elisio-17H dialyzer in subjects with ESRD who have been stable and receiving hemodialysis (HD) therapy at least 3 times a week for 3 months prior to enrollment.

4.1 Primary Objectives

The primary safety objective of this study is to demonstrate that performance of the Theranova 400 dialyzer compared to the Elisio-17H dialyzer is non-inferior, in regards to maintaining pre-dialysis serum albumin.

The primary efficacy objective of this study is to demonstrate that the Theranova 400 dialyzer has performance superiority to the Elisio-17H dialyzer in removing lambda immunoglobulin free light chains (λ FLCs).

4.2 Secondary Objectives

The secondary objectives of this study are to evaluate the performance of the Theranova 400 dialyzer compared to the Elisio-17H dialyzer in removing serum middle molecules, dialysis adequacy, levels of coagulation factors, and characterize monthly trends in pre-dialysis serum albumin levels.

4.3 Exploratory Objectives

The exploratory objectives for this study include:

- Evaluation of patient reported quality-of-life assessments.
- Evaluation of serum levels of the inflammatory marker high sensitivity C-Reactive Protein.

5. STUDY DESIGN AND CONDUCT CONSIDERATIONS

5.1 Study Design

This is a multi-center, prospective, randomized, controlled, open-label, parallel study to evaluate medically stable ESRD patients receiving dialysis treatment with either the Theranova 400 dialyzer or the Elisio-17H dialyzer for 3 sessions weekly, over 24 weeks.

A sufficient number of patients will be enrolled in the study in order to randomize 166 patients in a 1:1 manner to either the Theranova 400 dialyzer or the Elisio-17H dialyzer. The study will be conducted in up to 30 study centers in the USA.

The study will have an overall duration of approximately 27 weeks per patient. This period will consist of up to 2 weeks screening period, followed by a first treatment day visit and consequent three (3) dialysis sessions per week in an in-center setting over a 24-week period, at the end of the study there will be a visit occurring on the next HD session. The assessments will be performed on monthly basis.

5.2 Baseline Definition

Baseline measure for laboratory assessments and vital signs is defined as the last predialysis non-missing value obtained prior to dialysis on the day of the first study treatment. The final measure for laboratory assessments is defined as the last value captured during study treatment sessions (Week 24). If laboratory assessment on Week 24 is not applicable, the value on end of study visit (pre-dialysis) will be considered as final measurement.

Baseline measure for demographics, physical examination, general medical history and renal medical history is obtained during screening.

5.3 Sample Size

The sample size for this study is driven by the primary safety endpoint. The sample size calculation was performed using PASS® 15.0.1 software, procedure Non-Inferiority Tests for the difference between Two Means. Copyright© 2017, NCSS, LLC. All Rights Reserved. The power is based on a t-test with a one-sided alpha level of 0.025 where the true difference in means is assumed to be zero (0) and the non-inferiority margin is 5%.

Pre-dialysis serum albumin was not evaluated in the previous Theranova 400 dialyzer HD study, only the mass (G) of albumin in the dialysate was assessed. However, a study published in PLoS ONE⁶ did use a prototype of the Theranova dialyzer (MCO-CI) where in pre-dialysis albumin levels were collected after a month of therapy and, based on these data, a mean and standard deviation (SD) of 35.3 and 3.7 was observed. Comparable pre-dialysis albumin levels are expected with both study dialyzers and with a sample size of 70 patients per group, a t-test with a 0.025 one-sided significance level will have 80% power to demonstrate non-inferiority of the Theranova 400 dialyzer compared to the Elisio-17H dialyzer as assessed by pre-dialysis serum albumin with a non-inferiority margin of 5%. To allow for 15% of patients to drop out, a total of 166 patients will be randomized 1:1 to treatment with the Theranova 400 dialyzer or treatment with the Elisio-17H dialyzer (i.e., 83 patients per group).

A previously conducted Theranova 400 dialyzer prototype HDF study (Comparison of the Clinical Performance of Two Theranova 400 Dialyzer Prototypes in Hemodialysis Mode with the Performance of a High-Flux Dialyzer in Hemodialysis Mode and a High-Flux Dialyzer in High-volume Hemodiafiltration Mode – A Pilot Study, registered at clinicaltrials.gov, NCT02377622) was used to obtain λ FLC reduction ratio mean and standard deviation (SD) of 37.8 and 8.26. With a total sample size of 140 evaluable subjects as determined based on the primary safety endpoint (70 in the Theranova 400 dialyzer treatment group and 70 in the Elisio-17H dialyzer treatment group), a difference of 4.56 in the λ FLC reduction ratio in favor of the Theranova 400 dialyzer can be detected with 90% power at a two-sided 0.05 significance level using a two-sided two-sample t-test assuming equal variances. Including 15% drop out, a total sample size of 166 (83 per treatment group) need to be enrolled into this study.

The sample size calculation for the primary efficacy endpoint was performed using PASS® 15.0.1 software, procedure Two-Sample T-Test Assuming Equal Variance.

5.3.1 Justification of Non-Inferiority Margin

The 5% non-inferiority margin for reduction of albumin is based on two observational studies (Kalantar-Zadeh 2005⁷ and Mehrotra 2011⁸) in which a longitudinal analysis (change over time) of the association between serum albumin levels and mortality in large US cohorts of HD and PD patients, respectively, has been performed. Both studies controlled for underlying confounders of mortality by adjusting for comorbidities and Malnutrition-Inflammation Complex Syndrome. In both studies, variations in serum albumin levels of +/- 1 g/L over 6 months (corresponds to +/- 0.1 g/dL) have been defined as "stable serum albumin levels". A variation of +/- 1 g/L is a range with a width of 2 g/L, which is larger than 5% if applied to the reported mean baseline serum albumin levels. Therefore, a 5% variation in serum albumin can be justified as having no clinical significance.

The longitudinal analysis performed by Kalantar-Zadeh 2005 in 30,827 HD patients came to the conclusion that when comparing a reference group with serum albumin values in the range of 3.6 - 3.79 g/dL to groups of patients with ranges of serum albumin levels that were 0.2 g/dL (i.e. \geq 5% of the center of reference range) apart from the reference range, no increase in hazard ratio for all-cause and cardiovascular death was found.⁷

So, if we demonstrate statistically that the mean pre-dialysis serum albumin level of the Theranova group is unlikely to decrease by more than 5% after 24 weeks of therapy compared to control group, it can be hypothesized that the mortality risk associated with a decrement in serum albumin levels is not higher for the Theranova group. Therefore, a 5% non-inferiority margin is appropriate from a clinical point of view.

5.4 Randomization Procedure

All patients who sign the ICF will be assigned a unique patient identification number. Only patients confirmed to meet screening eligibility will be randomized and allowed to continue in the study. A sufficient number of patients will be enrolled in the study in order to randomize one hundred and sixty-six (166) patients across up to thirty (30) study sites.

The type of study dialyzer each patient will use during their treatment sessions will be determined according to a central randomization scheme provided by Baxter (via the Electronic Data Capture [EDC] system used for the study). Patients will be randomly assigned to receive one of the following two study dialyzers in a 1:1 ratio:

- Theranova 400 dialyzer
- Elisio-17H dialyzer

Randomization will be stratified by site and dynamic allocation will be used.

5.5 Schedule of Visits and Procedures

All clinical study evaluations will be performed according to the listed below. If a patient discontinues from the study prematurely, every attempt will be made to perform all of the procedures and evaluations that are scheduled for the final visit (i.e. end of study visit).

| | | Treatment Period | | | | | | | | | | | | | | |
|--|----------------------------------|-----------------------------------|-------------------|-------------------|-------------------|-------------------|-------------------|--------------------|-------------------|--------------------|-------------------|--------------------|-------------------|--------------------|-------------------|--------------------------|
| | Screen ing Visit Days - | Visit 1 1 st Treatn | ient Day | Visit 2 Week 4 | | Visit 3 Week 8 | | Visit 4 Week 12 | | Visit 5 Week 16 | | Visit 6 Week 20 | | Visit 7 Week 24 | | End of Study Visit |
| Evaluation | 14 to - 1 | Pre- dialysis | Post- dialysis | Pre- dialysis | Post- dialysis | Pre- dialysis | Post- dialysis | Pre- dialysis | Post- dialysis | Pre- dialysis | Post- dialysis | Pre- dialysis | Post- dialysis | Pre- dialysis | Post- dialysis | |
| Informed consent | Х | | | | | | | | | | | | | | | |
| Demographics | Х | | | | | | | | | | | | | | | |
| Medical histories (past and present) | х | | | | | | | | | | | | | | | |
| Physical examination including weight ^a | Х | | | | | | | | | | | | | | | х |
| Vital Signs | Х | Х | Х | Х | Х | Х | Х | Х | Х | Х | Х | Х | Х | Х | Х | Х |
| Randomization ^b | Х | | | | | | | | | | | | | | | |
| AE/SAE/ADE/PC° | Х | Х | Х | Х | Х | Х | Х | Х | Х | Х | Х | Х | Х | Х | Х | Х |
| Concomitant medications ^d | Х | х | х | х | x | х | х | x | х | х | х | x | х | х | х | х |
| HD prescription and Ultrafiltration ^e | x | | х | | x | | х | | х | | х | | Х | | х | |
| Body weight | Х | Х | Х | Х | Х | Х | Х | Х | Х | Х | Х | Х | Х | Х | Х | Х |
| Laboratory Evaluations ^f | Х | Х | | Х | Х | Х | Х | Х | Х | Х | Х | Х | Х | Х | Х | Х |
| Patient Reported outcomes ^g | | | Х | | | | | | Х | | | | | | Х | |

Table 1. Schedule of Visits and Procedures

Note: All sampling visits will be performed during the mid-week treatment.

^a Weight will be measured at screening and end of study, height will be measured only at screening.

^b Eligible patients will be randomized at the end of the Screening Period.

^c AEs, SAEs and PCs will be collected after the informed consent is signed and throughout the study, until the end of study visit. ADEs will be collected throughout the treatment period.

^d Medications will be collected throughout the study.

^e Ultrafiltration (U_F) will be obtained at the end of treatment of each 4 weeks treatment period.

^f Collection of laboratory samples is presented in the Schedule of Clinical Laboratory Evaluations below.

^g Patient reported outcomes (PROs) will include KDQOL-36 and EQ-5D-5L. All PROs will initially be assessed during the first treatment day, after 12 weeks of treatment and at the end of the study, following 24 weeks of treatment.

5.5.1 Schedule of Clinical Laboratory Evaluations

Table 2. Schedule of Clinical Laboratory Evaluations

| | | | Treatment Period | | | | | | | | | | | | | | | |
|-----------------------------|-----------------------------------|-------------------|--|-------------------|-------------------|-------------------|-------------------|-------------------|--------------------|-------------------|--------------------|-------------------|--------------------|-------------------|--------------------|-------------------|-----------------------|-------------------|
| | Screening Visit Days -14 to -1 | | Visit 1 1 st Treatment Day | | Visit 2 Week 4 | | Visit 3 Week 8 | | Visit 4 Week 12 | | Visit 5 Week 16 | | Visit 6 Week 20 | | Visit 7 Week 24 | | End of Study Visit | |
| Evaluation | Pre- dialysis | Post- dialysis | Pre- dialysis | Post- dialysis | Pre- dialysis | Post- dialysis | Pre- dialysis | Post- dialysis | Pre- dialysis | Post- dialysis | Pre- dialysis | Post- dialysis | Pre- dialysis | Post- dialysis | Pre- dialysis | Post- dialysis | Pre- dialysi s | Post- dialysis |
| β-hCG ^a | Х | | | | | | | | | | | | | | | | | |
| λ FLC ^b | х | | Х | | Х | Х | | | | | | | | | Х | Х | | |
| β2 Microglobulin | | | х | | х | х | | | | | | | | | х | Х | | |
| Serum Albumin | х | | X | | x | | х | | x | | х | | Х | | х | | x | |
| Liver function ^c | Х | | | | | | | | Х | | | | | | | | Х | |
| CFD ^d | | | Х | | Х | Х | | | | | | | | | Х | Х | | |
| IL-6 | | | Х | | Х | Х | | | | | | | | | Х | Х | | |
| ΤΝFα | | | Х | | Х | Х | | | | | | | | | Х | Х | | |
| κ FLC ^b | Х | | Х | | Х | Х | | | | | | | | | Х | Х | | |
| Vitamin A | | | Х | | Х | | | | | | | | | | Х | | Х | |
| BUN | Х | Х | | | Х | Х | Х | Х | Х | Х | Х | Х | Х | Х | Х | Х | | |
| Factor VII | | | Х | | | | | | Х | | | | | | Х | | Х | |
| Protein C | | | Х | | | | | | х | | | | | | Х | | Х | |
| Factor II | | | Х | | | | | | Х | | | | | | Х | | Х | |
| hs-C-Reactive Protein | x | | x | | x | | х | | x | | х | | х | | x | | | |
| Hematology ^e | Х | | Х | | | | | | Х | | | | | | | | Х | |

| HAV ^f , HBV ^g , HCV ^h , HIV ⁱ | х | | | | | |
|--|---|---|--|---|--|---|
| Coagulation ^j | х | | | X | | X |
| Serum phosphorus | x | x | | X | | x |
| Comprehensive metabolic panel ^k | x | x | | X | | X |
| Lipids ¹ | х | х | | Х | | X |

Notes: All sampling visits will be performed during the mid-week treatment.

A serum beta human chorionic gonadotrophin (β -hCG) will be performed within 3 weeks prior to the 1st treatment in the study for women of childbearing potential.

^a Female subjects of childbearing potential, defined as a woman <55 years old who has not had a partial or full hysterectomy or oophorectomy, must have a negative serum β-hCG pregnancy test at Screening. Subjects of childbearing potential must use a medically acceptable means of contraception during their participation in the study.

^b Lambda free light chains and Kappa free light chains

^c Include: Alkaline phosphatase (ALK-P), Alanine aminotransferase (ALT; SGPT), Aspartate aminotransferase (AST; SGOT), and Gamma-glutamyl-transferase (GGT), total bilirubin, direct bilirubin, globulin, total protein.

^d Complement Factor D

^e Includes: Hemotocrit, Hemoglobin, Mean corpuscular hemoglobin (MCH), Mean corpuscular hemoglobin concentration (MCHC), Mean corpuscular volume (MCV), Platelet count, Red blood cell (RBC) Count, White blood cell (WBC) Count with Differential

^f Hepatitis A Virus

^g Hepatitis B Virus

^h Hepatitis C Virus

ⁱ Human Immunodeficiency Virus

^j Includes: PT (INR), PT (Sec), aPTT

^k Includes: Sodium, Potassium, Chloride, Calcium, Bicarbonate, Glucose, Creatinine

¹ Includes: Total cholesterol, HDL cholesterol, LDL cholesterol, Triglycerides

5.6 Safety Measures

The primary safety endpoint is the pre-dialysis serum level of albumin after 24 weeks of treatment.

Secondary safety endpoints include:

- Pre-dialysis serum albumin measured on the first day of treatment and after every 4 weeks of treatment.
- Pre-dialysis Factor VII (MW = 50 kDa), Protein C (MW = 53-62 kDa) and Factor II (MW = 72 kDa) measured on the first day of treatment, after 4 weeks and after 24 weeks of treatment.
- Pre-dialysis Vitamin A measured on the first day of treatment, after 4 weeks and after 24 weeks of treatment.
- nPNA (nPCR) calculated after every 4 weeks of treatment.
- Change from baseline to final measure in chemistry and hematology laboratory tests (see Table 7 in Section 9.3).
- Monitoring of adverse events (AEs), serious adverse events (SAEs) and product complaints (PCs) for Baxter related devices.

5.7 Efficacy Measures

The primary efficacy endpoint is the Reduction Ratio (RR) of λ FLC after 24 weeks of treatment.

Secondary efficacy endpoints include:

- Reduction ratio of λ FLC measured on the first day of treatment and after 4 weeks of treatment.
- Reduction ratio of complement factor D (CFD; MW = 27 kDa), κ FLC (MW = 23 kDa), interleukin 6 (IL-6; MW = 25 kDa), tumor necrosis factor alpha (TNF α ; MW = 51 kDa), and β_2 -microglobulin (MW = 11.6 kDa) measured after 4 weeks and after 24 weeks of treatment.
- Change in pre-dialysis β_2 -microglobulin measured on the first day of treatment and after 24 weeks of treatment.
- Kt/V_{urea} measured after every 4 weeks of treatment.

5.8 Exploratory Measures

Exploratory assessments include:

- Inflammatory marker high-sensitivity C-Reactive protein (hs-CRP) measured predialysis on the first day of treatment and after every 4 weeks of treatment.
- KDQOL-36 measured on the first day of treatment, after 12 weeks and after 24 weeks of treatment.
- EQ-5D-5L measured on the first day of treatment, after 12 weeks and after 24 weeks of treatment.
- Changes in utilization for medication as cumulative dose for every 4 weeks' interval (i.e., erythropoiesis-stimulating agent (ESA), anti-hypertensive, iron and phosphate).

5.9 Completion and Discontinuation

Patients are considered withdrawn/prematurely discontinued from the study if their participation is discontinued before completion of the required evaluations as described in this protocol. Patients may be withdrawn/prematurely discontinued for any of the following reasons:

- 1. AE
- 2. Inadequate dialysis based on Investigator judgement
- 3. Protocol violations (i.e. the patient fails to meet protocol entry criteria or does not adhere to protocol requirements)
- 4. Pregnancy
- 5. Lost to follow-up (i.e. patient fails to return for study visits)
- 6. Voluntary withdrawal (i.e. patient's request)
- 7. Termination of study
- 8. Investigator's discretion
- 9. Renal transplantation
- 10. Switch to PD
- 11. Death
- 12. Change to another dialysis center, that is not a clinical study site
- 13. Missing 3 consecutive study treatments

14. Other reason (with reason noted on the electronic case report form [eCRF]) The Investigator may terminate a patient's study participation at any time during the study if he/she judges it to be in the patient's best interest. In addition, a patient may discontinue his or her participation any time during the study without having to justify his/her decision. If a patient's participation is discontinued, the reason(s) must be recorded in the source documents and on the eCRF. If a patient discontinues for any reason, every effort should be made to perform all of the procedures that are scheduled for the follow-up visit occurring at the pre-dialysis on the next treatment day. In addition, SAEs (related or not) and adverse device events (ADEs), will be followed until resolution or stable, including following the patient after the end of the study if necessary. The Investigator or designee should inform their site monitor the moment any patient is withdrawn or discontinued from the study, regardless of the reason(s) for withdrawal or discontinuation.

6. STUDY POPULATIONS

The study population consists of subjects with ESRD who have been stable and receiving hemodialysis (HD) therapy at least 3 times a week for 3 months prior to enrollment. A sufficient number of patients will be enrolled in the study in order to randomize one hundred and sixty-six (166) patients in a 1:1 manner to either Theranova 400 dialyzer or the Elisio-17H dialyzer. The study will be conducted in up to thirty (30) study centers in the USA.

6.1 Subject Disposition

The number of subjects who signed informed consent (enrolled), met the pre- and intraoperative inclusion and exclusion criteria (eligible), were randomized, and withdrew early will be displayed for subject disposition. Early withdrawals will be summarized according to primary reason for withdrawal. This table will be presented by treatment group and overall.

6.2 Analysis Populations

The full analysis set (FAS) will include all randomized patients.

The per-protocol set (PPS) will include all randomized patients who have received 24 weeks treatment with a study dialyzer without missing 3 consecutive study treatments (i.e. missing a full week of dialysis sessions) and do not have any major protocol violations that might impact the primary analyses.

The primary analyses will be performed on the FAS and supported by an analysis using the PPS. All other analyses will be performed on the FAS unless otherwise noted.

FAS is presented as-treated for analyses of

• AEs, SAEs, and Product Complaints

For other analyses including primary, secondary and exploratory endpoints, FAS is presented as-randomized.

6.3 Protocol Deviations

Protocol deviations will be classified as minor or major deviations and reviewed at a data review meeting.

Subjects with any major protocol deviation that may impact the primary endpoints will be excluded from the per-protocol analysis set, including the following:

- Violations inclusion and/or exclusion criteria
- Use of prohibited medication known to influence the primary endpoint
- Randomization or treatment errors
- Improper administration of study product
- Improper assessment of the primary endpoint
- Any other protocol deviations that may impact the primary endpoints

6.4 Subgroups

No subgroup analysis is planned for this study.

7. STATISTICAL ANALYSIS

The analyses described in this SAP refer to Amendment 5 of the Clinical Trial Protocol: 7905001 (dated 2018 FEB 09).

7.1 General

Unless otherwise noted, all analyses will be performed using SAS/GRAPH® 9.4 software, SAS/STAT® 14.1 software and Base SAS® 9.4. Copyright© 2002-2012, SAS Institute Inc. SAS and all other SAS Institute Inc. product or service names are registered trademarks or trademarks of SAS Institute Inc., Cary, NC, USA. All Rights Reserved.

Differences between treatment groups will be evaluated at a two-sided significance level of 0.050 (when rounded to 3 decimal places) and p-values < 0.050 will be considered statistically significant, unless otherwise noted.

The continuous data points will be summarized descriptively as mean, SD, median, min/max and categorical data points will be summarized as frequency and percentages.

7.2 Handling of Missing Data

7.2.1 General

Missed dialysis session visits will not be replaced. For dialysis sessions besides in Visit 8 Week 24, if a patient misses a mid-week dialysis session, where a study treatment visit was scheduled to occur, the missed study visit procedures will be performed during the next dialysis session and subsequent visits and follow-up visit will occur as planned. However, if the patient fails to return for that mid-week dialysis session and also misses the subsequent week (a third mid-week session), then the patient will be terminated from the study. Study termination also applies if the patient misses 3 consecutive study treatments (i.e. missing a full week of dialysis). Any dialysis session in Visit 8 Week 24 can not be collected behind schedule. Reasons for missed visits will not be captured separately but will be part of protocol deviation and/or as study discontinue reason if the patient being terminated from the study. Reasons for any other missing data besides missed visits will also be addressed via protocol deviations. A listing of protocol deviations will include a field showing whether the deviation lead to missing data. A protocol deviation table will summarize the number of missing data points in total and categorized by protocol deviation classification (major or minor).

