3.1 Overall Study Design and Plan

This is a multi-center, prospective, randomized, controlled, open-label, parallel study to evaluate medically stable ESRD patients receiving dialysis treatment with either the Theranova 400 dialyzer or the Elisio-17H dialyzer for 3 sessions weekly, over 24 weeks.

A sufficient number of patients will be enrolled in the study in order to randomize 166 patients in a 1:1 manner to either the Theranova 400 dialyzer or the Elisio-17H dialyzer. The study will be conducted in up to 30 study centers in the USA.

The study will have an overall duration of approximately 27 weeks per patient. This period will consist of up to 2 weeks screening period, followed by a first treatment day visit and consequent 3 dialysis sessions per week in an in-center setting over a 24 week period, at the end of the study there will be a visit occurring on the next HD session. The assessments performed, on a monthly basis, are shown in the Schedules of Evaluation in [Appendix 1](#) and [Appendix 2](#). Patients will initiate their HD treatment on their randomized study dialyzer, either Theranova 400 dialyzer or Elisio-17H dialyzer, at the midweek HD session (Wednesday or Thursday), and will then continue to have 3 dialysis sessions per week. During the treatment period, initial blood samples will be taken on the day of the first study dialyzer treatment and subsequent blood sampling samples will be taken after each 4 weeks of treatment, during the midweek HD session as illustrated in [Appendix 1](#). A scheme for the study is shown in [Figure 1](#) below. The overall duration of the complete study will be approximately 9 months to allow sufficient time for patient recruitment.

Figure 1. Trial Schematic^a

^a All study visits are performed during the mid-week treatment session.

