4.2 Inclusion Criteria

All of the following criteria must be met for the patient to be enrolled in this study.

1. ESRD patients age 22 and older, or between ages 18 and 21 with a weight ≥ 40 kg.
2. Clinically stable as judged by the treating physician and as demonstrated by stable medical history for 30 days prior to enrollment, physical examination, and laboratory testing.
3. Hemodialysis therapy with high-flux dialyzers for at least 3 months immediately prior to study enrollment and expected to survive for the next 12 months.
4. Expected to maintain an acceptable urea clearance (Kt/V) with a dialyzer of an approximate surface area of 1.7 m^2 .
5. Currently being dialyzed at an in-center setting, on a schedule of 3 times per week.
6. Able to give informed consent after an explanation of the proposed study, and who are willing to comply with the study requirements for therapy during the entire study treatment period.
7. Have a stable functioning vascular access (arteriovenous fistula, graft, or dual-lumen tunneled catheter); stable access will be confirmed by observed Kt/V ≥ 1.2 for past 2 measurements and/or achievement of within 15% the prescribed blood flow rate over 3 treatments prior to study entry.

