4.6 Missed Visits

In general, missed dialysis session visits will not be replaced. If a patient misses a mid-week dialysis session, where a study treatment visit was scheduled to occur, the missed study visit procedures will be performed during the next mid-week dialysis session and subsequent visits and follow-up visit will occur as planned. However, if the patient fails to return for that mid-week dialysis session and also misses the subsequent week (a third mid-week session), then the patient will be terminated from the study. Study termination also applies if the patient misses 3 consecutive study treatments (i.e. missing a full week of dialysis). Reasons for missed visits will be captured on the eCRF.

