Appendix 1 Formulas for Calculation of Endpoints Reduction Ratios (RR)

The RR for each solute, based on the change in the arterial plasma concentration over the dialysis session, will be calculated as:

$$RR (\%) = \left(1 - \frac{C_{Post}}{C_{Pre}}\right) \times 100$$

where C_{Pre} and C_{Post} are measured arterial plasma concentration of the solute before and after dialysis, respectively.¹

However, for the middle molecules (λ FLC and β_2 -microglobulin) C_{Post} will be first corrected (C_{Post-corr}) for the decrease in total extracellular volume due to fluid removal, as follows:

$$C_{Post-corr} = \frac{C_{Post}}{(1 + \frac{BW_{Pre} - BW_{Post}}{0.2 \times BW_{Post}})}$$

where C_{Post} is the measured plasma concentration of the solute after dialysis; and BW_{Pre} and BW_{Post} are the patient's body weight before and after dialysis, respectively.²

Kt/Vurea (quantification of hemodialysis treatment adequacy)

The linear equation used to calculate Kt/V_{urea} when applied to HD administered 3 times a week is as follows:

$$\frac{Kt}{V} = -\ln(R - 0.008 \times T) + (4 - 3.5 \times R) \times 0.55 \times \frac{Weightloss}{V}$$

where R is the ratio of post-dialysis to pre-dialysis BUN; V is the body water volume and Weightloss is expressed in the same units; and T is treatment time in hours.³⁴

¹ Krieter DH, Lemke HD, Wanner C. A new synthetic dialyzer with advanced permselectivity for enhances low-molecular weight protein removal. *Artif Organs*. 2008;32(7):547-554.

² Bergström J, Wehle B. No change in corrected β 2-microglobulin concentration after cuprophane haemodialysis. *Lancet.* 1987;1:628-629.

³ National Kidney Foundation. KDOQI Clinical Practice Guideline for Hemodialysis Adequancy: 2015 Update. *Am J Kidney Dis.* 2015;66(5):884-930.

⁴ Daugirdas JT. Second generation logarithmic estimates of single-pool variable volume Kt/V: an analysis of error. *J Am Soc Nephrol.* 1993;4(5):1205-1213.

nPNA (nPCR)

The below equations are used to calculate the midweek nPNA (PCR) when applied to HD patients is as follows:

$$nPNA (PCR) = \frac{C_0}{\left[25.8 + 1.15 \times \frac{spKt}{V} + \frac{56.4}{\frac{spKt}{V}}\right]} + 0.168$$

where C_0 is the pre-dialysis BUN.

SpKt/V is calculated as per below equation:

$$\frac{spKt}{V} = -Ln(R - 0.008 \times t) + (4 - (3.5 \times R)) \times \frac{UF}{W}$$

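### SAP 7.2.1 lets a missed mid-week visit be made up at any next dialysis session, contradicting the protocol and the SAP's own mid-week notes; nPNA is the one endpoint with a documented mid-week dependence

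*SAP*

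**What the plan says.** Protocol 4.6 (Missed Visits) states that, after a missed mid-week study visit, "the missed study visit procedures will be performed during the next mid-week dialysis session". SAP 7.2.1 repeats the rule with one qualifier gone: "the missed study visit procedures will be performed during the next dialysis session". Its next sentence deals with the case "if the patient fails to return for that mid-week dialysis session and also misses the subsequent week", and counts that as a third mid-week session.

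The notes under SAP Tables 1 and 2 carry no exception: "All sampling visits will be performed during the mid-week treatment". The protocol's Appendices 1 and 2 have the same note, and protocol 3.1 identifies mid-week as Wednesday or Thursday.

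Three other provisions bear on the point:

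- SAP 7.2.1 protects the final treatment visit: "Any dialysis session in Visit 8 Week 24 can not be collected behind schedule". Protocol 4.6 has no such bar.
- SAP 7.5 tabulates each value under its planned visit and defines no visit windows.
- SAP Appendix 1 introduces the nPNA formula with "The below equations are used to calculate the midweek nPNA (PCR) when applied to HD patients".

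SAP section 10, which lists departures from the protocol, does not mention the sampling-day rule.

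**The concern.** Pre-dialysis concentrations depend on the time since the last dialysis, which is why the plan fixes sampling at one point in the week. A make-up rule that allows any session removes that control for the displaced samples, and nothing later in the SAP recovers it. No interdialytic interval is derived, and a displaced sample keeps its planned visit label.

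The rule reaches Weeks 4 to 20. The exposed quantities are:

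- nPNA at five of its six post-treatment visits;
- the intermediate monthly albumin values in the secondary repeated-measures model;
- the Week 8 albumin SD that drives the sample size reassessment (SAP 7.3);
- the earlier albumin values that predict a missing Week 24 value (SAP 7.2.2), and a Week 20 value that may be carried forward in the LOCF sensitivity analysis (SAP 7.2.3).

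Because section 10 is silent, a reader cannot tell whether a change was intended or a word was lost.

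**Working it through.** The plan states no figure for this point, so there is none to reproduce.

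**The passages side by side**

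| Place | Session for the make-up sample |
|---|---|
| Protocol 4.6 | next mid-week session |
| SAP 7.2.1, make-up sentence | next session, any day |
| SAP 7.2.1, following sentence | presupposes mid-week |
| SAP Tables 1 and 2, notes | mid-week, no exception |
| SAP section 10 | no entry |

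The count to a third mid-week session works only if the make-up session is itself the second. The SAP's follow-on sentence therefore fits the protocol's rule and not the SAP's.

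**The gap before sampling.** Protocol 4.2 requires patients to be "Currently being dialyzed at an in-center setting, on a schedule of 3 times per week". Number the days from Monday = 1, so sessions fall on days 1, 3, 5 or on days 2, 4, 6.

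- Scheduled mid-week visit: 3 − 1 = 2 days; 4 − 2 = 2 days.
- Mid-week skipped, sampled at the next session (SAP wording): 5 − 1 = 4 days; 6 − 2 = 4 days.
- Mid-week skipped, later sessions attended, sampled at the next mid-week session (protocol): 10 − 8 = 2 days; 11 − 9 = 2 days.
- Ordinary weekend gap, for comparison: 8 − 5 = 3 days; 9 − 6 = 3 days.

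The SAP wording doubles the gap, provided that no replacement treatment is given in between.

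**Effect on nPNA.** SAP Appendix 1 gives nPNA = C0 / D + 0.168, with D = 25.8 + 1.15K + 56.4/K, where C0 is pre-dialysis BUN and K is spKt/V. The documents give no BUN values, so the following are assumptions: mid-week BUN of 40 to 70 mg/dL; K of 1.2, 1.4 and 1.6 with post/pre ratios R of 0.36, 0.30 and 0.26; K unchanged by the longer gap; and a linear BUN rise from a trough of C0 × R.

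Two days' rise is C0(1 − R). After four days BUN is C0·R + 2·C0(1 − R) = C0(2 − R), that is 1.64, 1.70 or 1.74 times the mid-week value. D is 74.18, 67.70 and 62.89 for the three values of K.

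| C0 | K | R | nPNA, 2-day gap | BUN, 4-day gap | nPNA, 4-day gap | Excess |
|---|---|---|---|---|---|---|
| 40 | 1.2 | 0.36 | 0.71 | 65.6 | 1.05 | 49% |
| 60 | 1.4 | 0.30 | 1.05 | 102.0 | 1.67 | 59% |
| 70 | 1.6 | 0.26 | 1.28 | 121.8 | 2.10 | 64% |

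The first and last rows are the extremes of the grid. Protein catabolism is held constant throughout, so the whole excess is artefact.

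**Effect on an arm comparison.** In the middle row an affected value is 1.67 − 1.05 = 0.62 too high. The between-arm difference at a visit shifts by 0.62 times the difference between arms in the fraction affected. The documents give no missed-visit rate. For assumed differences of 1%, 5% and 10% the shift is 0.006, 0.031 and 0.062. With equal fractions there is added noise but no bias.

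**The case against.** The strongest reply is that the SAP does not govern what sites do. Collection follows the protocol, protocol 11.9 allows deviation only in an emergency, and protocol 4.6 says mid-week. With the SAP's own next sentence still assuming a mid-week make-up, a dropped word is the likeliest explanation. This largely stands as an account of cause, and a reader should not infer that samples were in fact drawn after a doubled gap. It does not remove the contradiction: if sites follow the protocol, the SAP misdescribes its data and still has no rule for a sample taken off mid-week.

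The SAP wording could also be defended as keeping the sample near its planned date, 2 days late instead of 7. That is a possible reason for a change, but the SAP does not give it.

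On reach, the reply is right in three respects. Late collection is barred at Week 24, so observed primary endpoint values are untouched. The change in pre-dialysis β2-microglobulin runs from baseline to Week 24 and is equally protected. Kt/V is conditioned on three sessions a week and the reduction ratio on no weekday; both compare values within one session. It would be too strong to say that the plan's formulas in general cease to apply.

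A reader might also apply the plan's extracellular volume term (0.2 × body weight) to albumin and set the fall against the 1.765 g/L margin. The documents do not support that. The term is given for post-dialysis λ FLC and β2-microglobulin; the planning mean of 35.3 g/L is a pre-dialysis value that already contains the usual fluid gain; body weight and extra fluid would have to be assumed; and the margin concerns a difference in arm means at Week 24, not one patient's intermediate value.

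**Conclusion.** The contradiction is explicit and undeclared, and the SAP wording taken literally is a wrong rule, not a missing detail. Its documented analytic consequence is confined to nPNA at Weeks 4 to 20: an excess of about 49 to 64% for an affected patient-visit, given the assumed BUN, spKt/V and linear rise, and only where the mid-week treatment was skipped outright. The effect on arm means is likely to be small unless missed visits differ between arms.

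Intermediate albumin may shift too, and with it the Week 8 SD and the imputation predictors, but the size cannot be derived from the documents. A shift in a few Week 8 values would tend to raise the pooled SD. Since SAP 7.3 allows only an increase in sample size, the likely direction is towards more patients and not lost power.

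The documents do not support a reading in which the observed primary endpoints are compromised.

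**What to change.** 1. Reconcile SAP 7.2.1 with protocol 4.6 and the notes to Tables 1 and 2, so that one sampling-day rule holds throughout.
2. List any intended change in SAP section 10. The bar on late Week 24 collection belongs there as well, since protocol 4.6 does not contain it. In the same edit, correct the visit label: SAP 7.2.1 calls Week 24 Visit 8, while Tables 1 and 2 call it Visit 7.
3. For Weeks 4 to 20, flag every sample not taken at a mid-week session. SAP 9.3 already lists sample dates and times, so no new data are needed.
4. Do not apply the mid-week nPNA equation to flagged samples.
5. Compute the Week 8 albumin SD with and without flagged values, and say in advance which one sets the sample size.

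Removing flagged albumin values from the repeated-measures models or from the imputation is not part of this fix. It would create intermittent gaps, while the planned regression imputation relies on a monotone pattern.

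The cost is a wording change, one derived flag and a few missing intermediate nPNA values.
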